Protocol Title: GPR109A and Parkinson's Disease: Role of Niacin in Outcome Measures

Principal Investigator: [name]

1. Objectives

Describe the purpose, specific aims, and hypothesis:

(1) examine the blood, urine and spinal fluid of persons with Parkinson's to look for evidence of inflammation and; (2) whether 6 months of vitamin B3 supplementation may reduce the inflammation and/or improve symptoms.

2. Background

Describe the background and rationale for the study:

Inflammation plays a central role in Parkinson's disease (PD) pathology [1] as evidenced by the presence of microglia in the substantia nigra in post-mortem samples [2] as well as activated microglia and cytokines in clinical and animal studies [3]. The use of non-aspirin non-steroidal anti-inflammatory drugs was found to reduce the risk of PD [4]. We recently identified an anti-inflammatory receptor GPR109A that is upregulated in PD [5]. Niacin has a high affinity for this receptor, suggesting that it (niacin) may play an important role in reducing inflammation in PD. We also found that individuals with PD have a chronic niacin deficiency [5]. Using seed funding from the local PD chapter, we obtained pilot data which suggested that restoring the deficiency via over-the-counter (OTC) supplementation reduced inflammation and decreased the severity of the disease symptoms [6]. In this VA-funded study, we will determine the effect of 6 months' OTC niacin supplementation on inflammation (as assessed in the blood and spinal fluid) and severity of the PD symptoms.

References

1. Barnum CJ, Tansey MG (2010) Modeling neuroinflammatory pathogenesis of Parkinson's disease. *Prog Brain Res* 184: 113–132.
4. Gagne JJ, Powers MC (2010) Anti-inflammatory drugs and risk of Parkinson's disease: A meta-analysis. *Neurol* 74: 995–1002.

3. Inclusion and Exclusion Criteria

List the inclusion/exclusion criteria:

Inclusion criteria

PD subjects will be adult men and women diagnosed with idiopathic mild to moderately severe PD defined as modified Hoehn & Yahr Stages I-III (while "On"). PD is defined according to the UK Brain Bank Criteria made at least six months prior to recruitment to the study. PD features include the presence of at least two of the four cardinal clinical manifestations of the disease, which are tremor, rigidity, bradykinesia, and disturbances of posture or gait, without any other known or suspected cause of Parkinsonism. Subjects should be stabilized on PD medication for at least 3 months before enrollment into the study. Subjects' PD drug prescriptions will not be altered nor withheld during the study, i.e., they will be tested while "On." The patient will have signed informed consent. Subjects who do not have PD (i.e., healthy or have other medical conditions such as TBI, stroke, or other syndromes in which inflammation plays a role in the condition will also be recruited as control subjects. This will allow us to estimate whether these other conditions show similar or unique inflammatory profile.

Exclusion criteria

Subjects will be excluded if they had previous brain surgery or other severe neurological problems – intracerebral hemorrhage, traumatic brain injury, central nervous system malignancy, active CNS infection, significant stroke, Alzheimer disease or any type of implanted stimulator including but not limited to Deep Brain Stimulator (DBS) or pacemaker. All subjects must be without evidence of dementia, defined as a score > 24 the Mini-Mental State Examination and able to understand test instructions. Subjects must not have functional blindness (inability to participate in gait and visuomotor assessments) or lower limb amputation higher than the forefoot or any orthopedic problem that precludes performance of physical tests. Allergic to niacin. Significant cardiac, pulmonary, hepatic, gastrointestinal, or renal disease (e.g., New York Heart Association Class III or IV congestive heart failure; endocarditis; pulmonary insufficiency symptomatic at rest or with mild physical exertion; acute or chronic hepatitis; renal failure requiring dialysis; second and third degree AV block or sick sinus syndrome), or diabetes are also exclusionary factors.

4. Number of Subjects/Records/Samples Collected

Indicate the total number of subjects to be accrued/records reviewed/samples collected across all sites:

100

5. Recruitment Methods

Describe when, where, and how potential subjects will be recruited:

VA clinic (including medical records), word of mouth.

6. Procedures Involved

a. *Describe the procedures involved to include those procedures that are standard evaluation and/or care and those that are solely for research purposes:*

Standard procedures: basic physical examination for strength, speed, coordination, tremor, flexibility, rigidity and reaction time

Research procedures: questionnaire and tests to document health and cognitive status, blood, urine and spinal fluid samples, over-the-counter (non-prescription) vitamin B3 supplementation

b. Describe and explain the study design: Pre-post repeated measures placebo-controlled study

c. Describe the procedures performed to lessen the probability or magnitude of risks: Use of slow-release supplement to minimize potential skin itching

d. Describe the duration of an individual subject's participation in the study and the time involved: 6 months supplement study with a pre and post test, each lasting about 1 to 1.5 hr.

7. Data and Specimen Management


a. Describe the data analysis plan, including any statistical procedures: We will use the Unified Parkinson's Disease Rating Scale (UPDRS) III (Motor Section) as the primary pre- and post-treatment outcome assessment that is recommended for PD studies. Significant changes in outcome measures will be determined by performing a Mixed model analysis of variance, with Groups as the independent factor and Time as the repeated factor.
	 N/A												

b. When applicable, provide a power analysis: Based on the preliminary data using unpaired simple effects analyses, the minimum number of subjects needed per group to detect a statistical significance @ $p = .05$, 2-tailed and 80% power of detection are as follows:
 
  
 Outcome measures	Effect size (based on Cohen's d)	#	
   
 Subjects/group			
 
 UPDRS motor	1.46	14	
 
 Sleep efficiency (pilot data)	0.97	8	
  
 
The sample sizes are based on a large effect size, i.e., a grossly observable and clinically meaningful treatment effect. We have demonstrated that this is a reasonable expectation based on the actual effect sizes of the human preliminary data that we have shown. We used simple effects analyses as the basis for the sample size calculations because any sample size calculations based on the full design would require knowledge of the intra-class correlation across the treatments, as well as the carry-over, group, and period effects.
 
Correlation statistics. Based on the preliminary data's correlation coefficients (r) obtained via simple linear independent correlation tests comparing the variables versus disease severity (UPDRS motor section), the minimum number of subjects needed per group to detect a statistical significance @ $p = .05$, and 80% are as follows:
	Outcome measures	Effect size (based on Cohen's d)	#	Subjects/group			UPDRS motor	1.46	14	Sleep efficiency (pilot data)	0.97	8	 N/A
Outcome measures	Effect size (based on Cohen's d)	#											
Subjects/group													
UPDRS motor	1.46	14											
Sleep efficiency (pilot data)	0.97	8											

Outcome measures GPR109A levels Total Sleep Time Time to Fall Asleep Sleep Efficiency	r 0.59 -0.57 0.79 -0.73	# Subjects/group 20 18 8 10	

Based on the simple effects and correlation power analyses above, we propose to collect 30 PD subjects per group (total 60) to account for potential subject dropouts, experimental/data corruption and/or an unexpected increase in the variability of the data. We plan to recruit about 100 subjects to take into account potential drop-outs and an unexpected increase in the variability of the data which impacts the estimated statistical power.
			
c. Describe how data and specimens will be handled:			 N/A
i. What information will be included in that data or associated with the specimens?			
	Please refer to 6a above. All data will be coded.		
ii. Where and how data and/or specimens will be stored?			
	Specimens: Core lab. Data: Secured computer. ICD will be stored in a locked cabinet. NOTE: All data including specimens will be coded.		
iii. How long will the data and/or specimens be stored?			
	Indefinitely		
iv. Who will have access to the data or specimens?			
	Research team		
v. Who is responsible for receipt or transmission of the data and/or specimens?			
	[name] (PI)		
vi. How will data and/or specimens be transported?			
	Manually		

8. Provisions to Monitor the Data to Ensure the Safety of Subjects

This study involves no more than minimal risk study and this section is not required. **N/A**

The plan might include establishing a data monitoring committee and a plan for reporting data monitoring committee findings to the IRB and the sponsor.

a. *Describe the plan to periodically evaluate the data collected regarding both harms and benefits to determine whether subjects remain safe.*

Subjects will be contacted the day after their pre- and post-test participation in the study to make sure that they did not experience unexpected or severe reactions to the vitamin supplement and optional lumbar puncture. A log will be kept to document the contact and relevant information from the subject. Subjects will also be given a 24-hour hotline to report any adverse event that they think is related to the study.

b. *Describe what data are reviewed, including safety data, untoward events, and efficacy data.*

Safety and untoward events related to the vitamin supplement and optional lumbar puncture will be reviewed.

c. *Describe how the safety information will be collected (e.g., with case report forms, at study visits, by telephone calls with participants).*

Safety information will be collected by telephone calls or emails with the participants.

d. *Describe the frequency of data collection, including when safety data collection starts.*

Data will be collected by the researchers at baseline and the end of the study. Subjects will be instructed to contact the researchers as soon as possible if they experience any adverse events that they think is related to the study.

e. *Describe who will review the data.*

[name] will be the main person to review the data. He will consult with [name] or [name] if needed.

f. *Describe the frequency or periodicity of review of cumulative data.*

Cumulative data will be reviewed every month to ensure adherence to the approved protocol.

g. *Describe any conditions that trigger an immediate suspension of the research.*

If a subject reports an unexpected adverse event, the study will be suspended. The study will resume if it is determined that the event is unrelated to the study.

9. Withdrawal of Subjects

N/A

a. If applicable, describe anticipated circumstances under which subjects will be withdrawn from the research without their consent.
 
Click here to enter text.
	 N/A

b. If applicable, describe any procedures for orderly termination.
 
Click here to enter text.
	 N/A

c. If applicable, describe procedures that will be followed when subjects withdraw from the research, including partial withdrawal from procedures with continued data collection.
 
A subject who withdraws from the study on their own accord will be replaced by another. A subject who partially withdraws from procedures will remain in the study as long as they continue taking the supplement.
	 N/A

10. Risks to Subjects

a. List the reasonably foreseeable risks.

Low-level temporary discomfort or pain during the blood and lumbar draw. Contraindications for the lumbar puncture: Although there are no absolute contraindications to performing the procedure, caution will be used in patients with the following conditions: 1) Possible raised intracranial pressure; 2) Thrombocytopenia or other bleeding diathesis (including ongoing anticoagulant therapy); 3) Suspected spinal epidural abscess. The side effects associated with lumbar puncture may include following: 1) Discomfort or pain during the procedure; 2) Bleeding into the spinal cord, particularly in people who take blood thinners or have a low platelet count (thrombocytopenia); 3) Temporary headache as a result of CSF leakage; 4) Infection; 5) Nerve damage; 6) Cerebral herniation; 7) Temporary back pain.

We will take a conservative approach in deciding which patient to include from the lumbar procedure. Overall, [name] will exercise his clinical judgment to exclude a subject from the procedure if, in his opinion, he feels that the subject presents with a set of conditions which renders them unsuitable for the procedure.

b. If applicable, describe any costs that subjects may be responsible for because of participation in the research.
 
Click here to enter text.
	 N/A

c. If applicable, describe risks to others who are not subjects.
 
Click here to enter text.
	 N/A

11. Potential Benefits to Subjects

Describe the potential benefits that individual subjects may experience from taking part in the research.

Niacin is an over-the-counter supplement. Our preliminary data indicates that PD patients will benefit from the supplementation. The dosage selected is 250 mg daily dose for 6 months. These dosages are low and do not produce any side effects. If at all, the PD patients will be benefitted by its actions. Subjects will be given a \$50 gift card for successfully completing the 6-month study. They will receive an additional \$100 if they participate in the spinal draw. At the end of the study, all subjects will receive the real niacin and be invited back for an optional follow-up assessment.

12. Confidentiality

Describe the procedures for maintenance of confidentiality.

All data will be kept in locked files and information on computer databases including cloud storage will be coded to protect patient identity. The only place where the subject's identity is revealed is the Informed Consent form. Subjects' identity will be coded in all other sources of documentation (hard copies and electronic files).

13. Consent Process

If you are obtaining consent of subjects describe the consenting process.

Subjects who indicate an interest to participate in this study will be tested at the VA clinic and/or visit [name] ground-floor Human Movement Science lab on the GRU campus. Blood and urine samples will be obtained in the adjacent room in the Interdisciplinary Clinical Practice facility. The nature of the information in the informed consent will be a brief overview of the study, tests involved, benefit and risks as well as the subject's right to terminate the session at any time. The informed consent will also state that each participant agrees to freely and voluntarily participate in the study. The document will also state that any other financial impact is the participant's sole responsibility.

14. Compensation for Research-Related Injury

This section is not required when research involves no more than Minimal Risk to subjects. **N/A**

a. *Describe the available compensation in the event of research related injury.*

Click here to enter text.

15. Resources Available

N/A

a. *Describe the availability of medical or psychological resources that subjects might need as a result of an anticipated consequences of the human research.*

Click here to enter text.

b. *Describe your process to ensure that all persons assisting with the research are adequately informed about the protocol, the research procedures, and their duties and functions.*

Documentation from the VA facility will be provided that research team members have undergone training in the following areas: Good clinical Practices; the ethical principles of

human research protection; Privacy; Cybersecurity; and VA Research Data Security and Privacy.

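### The primary UPDRS III is scored once before and once after with 'On' as the only rule for drug state; matching the time since the last PD dose within each subject would cheaply remove avoidable variance.

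*Combined protocol and SAP*

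**What the plan says.** Section 7a names the UPDRS motor section "as the primary pre- and post-treatment outcome assessment that is recommended for PD studies". Section 6d describes a "6 months supplement study with a pre and post test, each lasting about 1 to 1.5 hr". The primary comparison therefore rests on one score per subject at each end. Section 11 mentions an optional follow-up, but it comes after every subject has received niacin and adds nothing to the placebo comparison.

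The inclusion criteria in Section 3 deal with PD medication in two sentences. On entry: "Subjects should be stabilized on PD medication for at least 3 months before enrollment into the study". During the study: "PD drug prescriptions will not be altered nor withheld during the study, i.e., they will be tested while" On. No section gives an interval since the last PD dose, asks for that interval to be the same at both visits, or describes a check that the subject is On. The exclusion criteria do not mention motor fluctuations, and modified Hoehn & Yahr stages I to III are eligible. The procedures listed in Section 6a do not name a record of PD drugs or dose times.

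Section 6b calls the design a "Pre-post repeated measures placebo-controlled study". Section 7a plans a "Mixed model analysis of variance, with Groups as the independent factor and Time as the repeated factor", with no term for dose timing or PD drugs. Section 7b gives an effect size of 1.46 for UPDRS motor and 14 subjects per group, then plans 30 PD subjects per group.

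**The concern.** A motor score taken in the On state reflects both the disease and how well the drug is working at that hour. If a subject is seen at one point in the dose cycle before treatment and at another point 6 months later, the difference between those points is part of the measured change. With a single score at each visit, nothing averages it out.

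Two things are at stake. The first is precision: timing error that is alike in both groups widens the spread of change scores and lowers power. The second is conditional: if one group is tested systematically closer to a dose than the other at the post-test, the difference between groups is biased.

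A related gap is that the plan relies on prescriptions staying as they are for 6 months but names no step that would show whether they did. Dose times and prescription changes that are not written down at the visit may be hard to recover later.

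**Working it through.** **Inputs from the documents.** Effect size d = 1.46 for UPDRS motor, two-sided 0.05, 80% power, unpaired comparison, 14 per group stated, 30 per group planned (Section 7b).

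**Inputs that are assumptions.** The documents give no SD and no figure for dose-timing error. I take an SD of change under matched timing, s0, of 6 to 10 points, and an independent timing error with SD e of 2 to 5 points at each visit, alike in both groups. I also take 30 evaluable subjects per group, and treat d as the mean difference divided by s0.

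**The plan's own figure.** A two-sample t-test with d = 1.46, two-sided 0.05 and 80% power needs 9 per group (8.44 before rounding up), not 14; 14 per group gives 96% power. This mismatch is a separate matter. What follows uses only d = 1.46 and 30 per group.

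**Step 1: variance of change.** Timing error enters at both visits, so SD of change = √(s0² + 2e²).
- s0 = 10, e = 2: variance 100 + 8 = 108, ratio 1.08.
- s0 = 8, e = 3: variance 64 + 18 = 82, SD 9.06, ratio 1.28.
- s0 = 8, e = 4: variance 64 + 32 = 96, SD 9.80, ratio 1.50.
- s0 = 6, e = 5: variance 36 + 50 = 86, ratio 2.39.

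The rise therefore runs from 8% to 139%, with 28% to 50% in the middle of the range.

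**Step 2: power at 30 per group.** The effective effect size is d′ = d / √(variance ratio), and the noncentrality of the t-test is d′ × √(30/2) = 3.873 d′.

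| d under matched timing | No timing error | Variance ×1.28 | Variance ×1.50 | Variance ×2.39 |
|---|---|---|---|---|
| 1.46 (the plan) | >99.9% | 99.8% | 99.5% | 95% |
| 1.0 | 97% | 92% | 87% | 69% |
| 0.8 | 86% | 77% | 70% | 50% |
| 0.74 | 80% | 70% | 63% | 44% |

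The value 0.74 (0.736 before rounding) is the smallest effect that 30 per group detects with 80% power. It is not a figure from the plan, and any added noise takes its power below 80% by construction.

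**Step 3: how much noise the plan can absorb.** At d = 1.46, power at 30 per group falls to 80% when the variance has risen by (1.46 / 0.736)² − 1 = 2.94, that is by 294%. The largest rise in the assumed range is 139%.

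**Step 4: if timing differs between groups.** With no true effect and a systematic difference of b SD between groups, the rejection rate of the two-sided 5% test at 30 per group is 6.7% for b = 0.1, 11.9% for b = 0.2 and 20.8% for b = 0.3. Nothing in the documents indicates that such a difference exists; these figures show only what it would do.

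**The case against.** The strongest objection is that the plan can afford this noise. At its own effect size, power stays at about 95% or more over the whole assumed range. Section 7b also raises 14 per group to 30 partly to allow for greater variability than expected. That stands. In addition, the preliminary SD behind 1.46 may already contain On-state timing noise; if so, Step 2 counts it twice and matching would be a gain over the plan, not the repair of a loss. The limit to the objection is that 1.46 comes from preliminary data, and the loss is material if the true effect is nearer 0.8.

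A reader might infer that timing noise will be mistaken for a niacin or placebo effect. The documents do not support that. There is a placebo group, the comparison is of change between groups, and noise alike in both adds variance without creating a difference. The documents describe neither randomisation nor blinding, so balance in timing is not assured, but that shows only that bias is possible.

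A reader might also infer that PD drug changes will be absorbed as ordinary results, or that increases will cluster in the group doing worse. Section 3 says prescriptions will not be altered, so a change would be a departure from the plan, and nothing in the documents bears on where changes would fall. It would also go too far to say that PD drugs will go unrecorded: Section 6a lists a questionnaire and tests on health status, and a data form not shown here may hold a medication field. What stands is that the protocol does not require the record.

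Finally, 'On' is a real restriction. A subject whose dose has worn off does not meet it, so only variation within the On state is at issue.

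**Conclusion.** The point holds as a cheap improvement, not as a flaw that threatens the primary result. Unmatched dose timing adds variance to a change score built from two single measurements; it would become bias only if timing differed between groups.

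The size rests on assumed SDs, on independent timing errors alike in both groups, and on 30 evaluable subjects per group. If the true effect is near 1.46, the loss is negligible. If it is about 0.8 or less, timing error in the middle of the assumed range costs roughly 9 to 17 percentage points of power (86% to 77–70% at 0.8; 80% to 70–63% at 0.74). The prescription part is the weaker half: it is a matter of being able to check a statement the plan already makes.

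**What to change.** In Sections 3 and 6d, state that each subject's post-test UPDRS III is done at the same interval after the last PD dose as that subject's pre-test, within a stated window (30 minutes, for example). Record the time of the last dose and the time of the test at both visits. Matching the interval is enough; requiring the same clock time as well could be unachievable if a subject's dose times move over 6 months.

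At both visits, copy the current PD prescription, so that the statement in Section 3 can be checked. In Section 7a, say that all subjects stay in the primary comparison whatever happened to their prescription, and that the number with a changed prescription will be reported by group. I would not add an analysis that counts a drug increase as a poor outcome: for a continuous score it would need a rule for the value to assign, and the plan offers no basis for one.

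The cost is less flexible appointments and a few extra data fields at each visit. No visit or procedure is added, and no rule on PD drugs changes.

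### Non-study vitamin B3 is not excluded, restricted or stated to be recorded, so own use can pull the niacin-versus-placebo contrast toward no effect

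*Combined protocol and SAP*

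**What the plan says.** Section 3 excludes a long list of neurological, cardiac, pulmonary, hepatic, renal and other conditions. The single item that concerns the study product is "Allergic to niacin". The stability rule in the same section covers Parkinson's drugs: "Subjects should be stabilized on PD medication for at least 3 months before enrollment into the study". So does the rule for the study period: "Subjects' PD drug prescriptions will not be altered nor withheld during the study". Neither mentions supplements.

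Section 6a describes the intervention as "over-the-counter (non-prescription) vitamin B3 supplementation", and Section 6b gives the design as "Pre-post repeated measures placebo-controlled study". The rationale in Section 2 is that "We also found that individuals with PD have a chronic niacin deficiency", with pilot data suggesting that "restoring the deficiency via over-the-counter (OTC) supplementation reduced inflammation and decreased the severity of the disease symptoms". Section 11 adds: "Niacin is an over-the-counter supplement. Our preliminary data indicates that PD patients will benefit from the supplementation".

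A low niacin level is not an entry criterion. The analysis in Section 7a has Groups and Time as its factors, with no term for B3 intake. Section 7b proposes 30 Parkinson's subjects per group.

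**The concern.** The trial compares people given niacin with people given placebo, and part of its reasoning is that the niacin group has a deficiency to correct. Anyone can buy the product. Applied as written, the criteria admit a person who already takes it, and nothing asks a placebo subject to refrain from starting it.

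Two groups would then weaken the comparison: steady users allocated to niacin, who may have less room to change, and placebo subjects who begin their own B3 during follow-up. Both push the UPDRS III contrast toward zero. Prior use also enters the first objective, because it can shift the baseline inflammatory markers and GPR109A, which Section 7b correlates with disease severity. After a null result, the sponsor would find it hard to separate an ineffective product from a comparison in which part of both arms had been exposed.

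**Working it through.** **1. The plan's own figure.** Section 7b gives d = 1.46 for UPDRS motor, two-sided .05, 80% power, unpaired, and a minimum of 14 per group. An unpaired t-test at these inputs needs 9 per group (8.44 before rounding; 8 by normal approximation), and 14 per group has 96% power. So the 14 does not reproduce. That is a separate matter. The calculation below uses the 30 per group actually proposed.

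**2. Who dilutes the contrast.** Let d be the niacin effect on change (post minus pre) in SD units. Assume that a subject already exposed gains nothing from added niacin.
- Steady user on niacin: change 0 instead of d. If these are a share a of the niacin arm, its mean change is (1 − a)d.
- Steady user on placebo: exposed at both tests, so change is 0, as for any other placebo subject. Nothing is lost.
- Placebo subject who starts B3 after the pre-test: change d. If these are a share b of the placebo arm, its mean change is bd.

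The difference in change is (1 − a)d − bd = (1 − c)d, with c = a + b. If own use removes only part of the effect, c is smaller.

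**3. Power.** The unpaired t-test with n = 30 per group has 58 degrees of freedom and noncentrality (1 − c)d × √(30/2) = 3.873(1 − c)d. The SD is held at 1. The documents give no value for c, so the shares are assumptions. Three effects are shown: the plan's 1.46; 0.8 as an illustrative smaller effect; and 0.74 (0.736 unrounded), which 30 per group detects with 80% power.

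| c | d = 1.46 | d = 0.8 | d = 0.74 |
|---|---|---|---|
| 0 | >99.9% | 86% | 80% |
| 10% | 99.9% | 78% | 71% |
| 20% | 99.4% | 68% | 61% |
| 30% | 97.3% | 57% | 50% |
| 50% | 79% | 33% | not shown |

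Example: d = 0.8 and c = 20% give 0.64 × 3.873 = 2.48.

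**4. Where power crosses 80%.** This happens when (1 − c)d = 0.736. For d = 1.46, c = 1 − 0.736/1.46 = 50%. For d = 0.8, c = 1 − 0.736/0.8 = 8%.

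**5. Attenuation and sample size.** Whatever d is, the estimate shrinks by the factor (1 − c). At c = 20%, a true 1.46 is estimated as 1.17. Holding power constant multiplies the required sample by 1/(1 − c)²: 1.23 at 10%, 1.56 at 20%, 2.04 at 30%.

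**The case against.** The strongest reply is that the loss of power depends on the effect chosen. At the plan's own d = 1.46, power at 30 per group stays above 97% with 30% dilution, and the plan has already gone from a stated minimum of 14 to 30 per group, a factor of 2.1. This stands. At that effect the damage is to the size of the estimate, not to the chance of a significant result. It does not close the gap, because Section 7b itself allows for more variable data than expected, which would lower d.

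The mechanism is also narrower than it first appears. A reader might infer that every B3 user in either arm removes contrast. For a pre-post Groups-by-Time analysis that is wrong: a steady user on placebo is exposed at both tests and leaves the change contrast intact. Such a subject would matter only if the arms were compared at post-test alone.

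The no-added-benefit assumption can be disputed too. Section 2 rests the rationale on niacin's affinity for GPR109A as well as on deficiency, so a user with adequate niacin might still respond. Nothing in the documents suggests that self-supplementation is common. Section 11 promises all subjects niacin at the end of the study, which may weaken the motive to buy it meanwhile. These points limit the likely size; none shows that use is absent.

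Finally, a reader might infer that own use could never be detected. That goes too far. Section 6a lists a health questionnaire without its items, Section 5 mentions medical records, and Section 7c keeps specimens indefinitely. Some use might be found later. The supportable statement is that the protocol does not commit to recording it.

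**Conclusion.** The gap is real. Allergy is the only niacin-related exclusion, and the documents neither bar current B3 users, nor restrict non-study B3 during the 6 months, nor state that use is recorded. The direction is toward no effect, through steady users on niacin and placebo subjects who start B3, and the baseline markers are affected as well.

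The size cannot be computed from the documents. It rests on an assumed share c, on users gaining nothing from the study product, on a constant SD, and on all 30 per group being analysed. Under those assumptions the consequence runs from an attenuated estimate with little loss of power (d = 1.46) to a material loss (68% power at d = 0.8 and c = 20%).

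A reader might conclude that the trial is underpowered because of this omission. The documents do not support that: at the planned effect, dilution would have to reach about half before power fell below 80%. This is an inexpensive improvement to the central contrast, not a fatal flaw.

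**What to change.** - **Eligibility.** Add to the exclusion criteria in Section 3: current use of a separate vitamin B3 supplement (niacin, nicotinamide or related) at screening. Which products count, and how recent use must be, is for the investigators to define.
- **During the study.** Ask subjects not to start non-study B3 in the 6 months. The screening exclusion alone does not address placebo subjects who start later.
- **Recording.** Add one item on non-study B3 use to the existing questionnaire, at pre-test and at post-test.
- **Analysis.** Keep all subjects in the primary analysis as allocated. An analysis without those who report use should be supportive only, with the caveat that use begun after allocation may differ by arm, so dropping those subjects can introduce selection.

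The cost is one eligibility line, one request to subjects and one questionnaire item, with no added visit or procedure. A few candidates become ineligible, and the results then apply to people not already taking B3.
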